9. SAFETY ANALYSES

All safety analyses will be conducted on the ITT Cohort. The total number of serious adverse events (SAEs) and adverse events (AEs) will be summarized for each randomization arm by severity grade as shown in Mock Table 1. A line listing of SAEs will be presented by randomization arm. Attribution for SAEs and AEs as related or not related to the study medication as assessed by the clinical monitor will be reported. Social harms will be summarized for each randomization arm.

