2.2. STUDY OBJECTIVES AND ENDPOINTS

This document focuses on the statistical procedures for the primary and secondary objectives and endpoints listed in the following table.

Objectives	Endpoints
Primary	
To test the efficacy of HCQ (400 mg orally daily for 3 days then 200 mg orally daily for an additional 11 days, to complete 14 days) to prevent incident SARS-CoV-2 infection, compared to ascorbic acid among contacts of persons with SARS-CoV-2 infection	Polymerase chain reaction (PCR)-confirmed SARS-CoV-2 infection through Day 14
Secondary	
To determine the safety and tolerability of HCQ as SARS-CoV-2 PEP in adults	Adverse events
To test the efficacy of HCQ (400 mg orally daily for 3 days then 200 mg orally daily for an additional 11 days, to complete 14 days) to prevent incident SARS-CoV-2 infection two weeks after completing therapy, compared to ascorbic acid among contacts of persons with SARS-CoV-2 infection	Polymerase chain reaction (PCR)-confirmed SARS-CoV-2 infection through Day 28
To test the efficacy of HCQ to shorten the duration of SARS-CoV-2 shedding among those with SARS-CoV-2 infection in the HCQ PEP group	SARS-CoV-2 viral shedding by PCR
To test the efficacy of HCQ to prevent incident COVID-19	PCR-confirmed COVID-19 diagnosis post start of HCQ therapy

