5. TRIAL PARTICIPANT DISPOSITION

5.1. DISPOSITION OF PARTICIPANTS

Relevant to the analyses described in this SAP, a CONSORT flow diagram will be constructed to describe how all of the participants who entered the study are accounted for including the following measures, as applicable:

The numbers of participants screened, screened out (with reasons for exclusion), enrolled, randomized, allocated to each study arm, received assigned intervention (with reasons for not receiving assigned intervention), reasons for discontinuation from follow-up (e.g., lost to follow-up, adverse event, noncompliance, etc.), and the number of participants with available data for each assay.

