5.2. TREATMENT EXPOSURE

Self-reported pill taking will be reported by prescribed dosing day stratified by arm and overall. The summary measures will be number of doses reported taken and number of doses reported taken divided by number prescribed. The number and proportion of adherent participants will be reported by day and overall time.

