PCR tests not meeting these criteria will be referred to as negative. The endpoint will be defined as the number of days from the first positive test until virus is no longer detected (a negative test has been observed with no positive tests following). Censoring will be indicated if the participant is still shedding on day 14. Participants who have a COVID-19 related hospitalization or death will be assumed to shed through day 14 and would have their days of shedding censored as if they had been observed through day 14.

Analysis Details: We will use a Cox Proportional Hazards model with robust standard errors to estimate the hazard ratio and corresponding 95% confidence interval and Wald test statistic. Robust confidence intervals and p-values will be displayed. This analysis represents a subset selected post-randomization and therefore requires adjustment for confounders. Due to lack of known confounders early in the epidemic, we propose that the list of baseline descriptors be assessed individually for their association with the primary endpoint. Those associated univariably with $p < 0.10$ will be included in this analysis. A hazard ratio greater than 1 (treatment/control) indicates efficacy of the intervention in shortening shedding.

Prevention of COVID-19 diagnosis

Objective: To test the efficacy of HCQ to prevent incident COVID-19.

Outcome: PCR-confirmed COVID-19 diagnosis post start of HCQ therapy through Day 14

Cohort(s): ITT, mITT, Sensitivity, Seronegative, Infected

Definition of Endpoint: COVID-19 is defined as symptomatic disease based on the following criteria with virologic confirmation (RNA PCR Ct \leq 40):

- At least TWO of the following symptoms: Fever ($\geq 38^{\circ}\text{C}$), chills, rigors, myalgia, headache, sore throat, new olfactory and taste disorder(s), OR
- At least ONE of the following symptoms: cough, shortness of breath or difficulty breathing, OR
- Severe respiratory illness with at least 1 of the following:
 - Clinical or radiological evidence of pneumonia, OR
 - Acute respiratory distress syndrome (ARDS)

A participant will be defined as having reached the endpoint if they have the diagnosis above. The time of the endpoint will be the onset of symptoms. Participants who do not have the endpoint will be censored at the last time they were known to be symptom-free. Death and hospitalization will be counted in the endpoint.

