10. CHANGE HISTORY

This section will Identify major changes, if any after version 1.0 approval.

Version	Activity Description
---------	----------------------

Number	Effective Date	Affected Section(s)	

Mock Table 1. Total Number of Serious Adverse Events, by Severity Grade and Arm

Severity Grade	Randomized Arm					
	HCQ		Control		Total	
	n	%	n	%	n	%
Grade 1 / mild						
Grade 2 / moderate						
Grade 3 / severe						
Grade 4 / potentially life-threatening						
Grade 5 / death						

NOTE: The denominator for calculation of percentages is the number of SAEs at a given severity level with the exception of the 'Total' column, for which the denominator is the total number of SAEs.

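### SAP 9 tabulates adverse events as event totals by grade and arm; no planned summary gives the participants affected per arm, and nothing shows the type of non-serious AEs

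*SAP*

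**What the plan says.** The SAP lists as a secondary objective "To determine the safety and tolerability of HCQ as SARS-CoV-2 PEP in adults", with adverse events as the endpoint (SAP 2.2). Protocol 11.3.2 says that AEs will be compared between study groups.

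SAP 9 puts safety on the ITT Cohort and states that the totals of SAEs and "adverse events (AEs) will be summarized for each randomization arm by severity grade as shown in Mock Table 1". The shell is titled "Total Number of Serious Adverse Events, by Severity Grade and Arm". It has grade rows, and an n and a % column for each arm and for the total. Its note reads: "The denominator for calculation of percentages is the number of SAEs at a given severity level". The Total column uses all SAEs as its denominator.

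SAP 9 also plans relatedness of SAEs and AEs, a summary of social harms and one listing: "A line listing of SAEs will be presented by randomization arm". Elsewhere, SAP 5.1 plans a CONSORT diagram with reasons for leaving follow-up, where an adverse event is one example. SAP 5.2 plans adherence: "Self-reported pill taking will be reported by prescribed dosing day stratified by arm and overall".

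Protocol 10.2 puts two kinds of AE on the eCRF: SAEs, and AEs that the participant or a clinician judges to be associated with study medication. Protocol 7.2.1 expects mainly gastrointestinal symptoms and transient rash. It also mentions minor blurred vision, which may come with mild headache, and hypoglycaemia. Protocol 7.4 has management rules for gastrointestinal disturbance, visual disturbance and allergic reaction.

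**The concern.** Someone weighing HCQ for well but exposed contacts asks two questions: how many people in each arm had a suspected reaction, and of what kind? The planned tables count events, and their percentages describe how events divide between arms. An arm with a few people who report many episodes looks the same as an arm with many people who report one each.

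Type is lost as well. The expected HCQ reactions are mostly non-serious and fall into a few named kinds, but rows by grade pool them with everything else. An excess of one kind is diluted in a total over all kinds, and for non-serious AEs there is no listing to go back to.

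**Working it through.** There is no planned figure to reproduce, so the check is of what the layout can and cannot show. The documents give no AE rates for this regimen. Protocol 7.2.1 mentions rash in 10% of participants, but often with a sustained loading dose, which this trial avoids. All rates below are therefore assumed.

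**1. What a percentage means.** Share for HCQ = HCQ events / (HCQ + control events) at that grade. The two arm shares always sum to 100%. With 6 v 4, 60 v 40 or 300 v 200 events, the percentages are 60% and 40% each time. The n columns distinguish these cases, and n divided by arm size gives events per participant.

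**2. What n cannot show.** Take 60 HCQ and 40 control events with 620 per arm. That is half of the 1240 baseline-negative participants in SAP 2.4, which follows from 93 / ((0.10 + 0.05)/2) = 1240. The printed row is the same in all of these cases:

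| People affected, HCQ v control | Risk | Risk ratio |
|---|---|---|
| 60 v 40 | 9.7% v 6.5% | 1.50 |
| 40 v 40 | 6.5% v 6.5% | 1.00 |
| 30 v 40 | 4.8% v 6.5% | 0.75 |
| 20 v 40 | 3.2% v 6.5% | 0.50 |

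The last row needs an average of three events per affected person on HCQ and one on control. If repetition were equal in the two arms, the ratio would stay at 1.50 and only the absolute risks would be wrong.

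**3. Dilution of type.** Assume one event per affected person and type, gastrointestinal AEs in 6% v 2%, and other types in 6% of both arms. The total is 12 v 8 per 100, a ratio of 1.5, although the gastrointestinal ratio is 3.0. With other types at 2% the total is 8 v 4 (ratio 2.0); at 10% it is 16 v 12 (ratio 1.33).

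**4. How precise a participant table would be.** The 95% half-width is 1.96 × √(DE × [p1(1−p1) + p2(1−p2)]/n). DE is the design effect for household randomisation, 1 + (m_w − 1) × ICC, with m_w = Σm²p/Σmp. The hypothetical rows of Protocol Table 1 give m_w = 2.47/1.35 = 1.83 (A), 2.62/1.40 = 1.87 (B) and 7.92/2.50 = 3.17 (C). With ICC assumed at 0 to 0.2, DE runs from 1.0 to 1.43.

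The size reached is uncertain. SAP 8.1 has four interim looks with a binding futility bound, and the third is at 56 expected events. With no effect and a 10% attack rate in both arms, that is 56/0.10 = 560 baseline-negative participants, or 280 per arm. ITT also includes baseline-positive contacts, whose number is unknown. The other sizes are 620 per arm and 1000 (half of the cap of 2000).

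| Assumed risks | n = 280 | n = 620 | n = 1000 |
|---|---|---|---|
| 1% v 3% | 2.3 to 2.8 | 1.6 to 1.9 | 1.2 to 1.5 |
| 5% v 10% | 4.3 to 5.2 | 2.9 to 3.5 | 2.3 to 2.7 |

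Entries are half-widths in percentage points, for DE 1.0 to 1.43.

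**The case against.** Several things can fairly be said for the plan.

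- **SAEs are partly covered.** A reader might infer that people with an SAE cannot be counted by arm. The documents do not support that: the listing by arm may allow a count by hand and would show what each event was, although its columns are not specified. What is missing for SAEs is a planned summary.
- **The note names SAEs only.** A reader might take the event denominator as expressly fixed for AEs. It reaches them only because SAP 9 sends AEs to the same shell. If the note is held not to apply, non-serious AEs have no specified denominator, and the gap stays.
- **The n is printed.** A reader might infer that the layout hides how frequent events are. It does not. With one event per person, n over arm size is the participant risk; information is lost through repeats.
- **SAP 4 promises frequencies and relative frequencies for categorical variables.** This is a general rule that names no AE variable and no unit, and the table's own note is more specific.
- **The CONSORT diagram counts people who leave because of an AE.** Under Protocol 8.1, participants who stop treatment stay in follow-up, so most suspected reactions would not appear there. Adherence by arm is only an indirect sign of tolerability.
- **The table can be made at reporting, and it shows suspected reactions only.** Both are true. Taste is only partly masked (Protocol 7.6), so the judgement of association may differ by arm. Event totals carry the same limit.

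What stands against the point is its weight: no primary estimate, error rate or data collection is touched.

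**Conclusion.** The point holds as a fault in the safety tables. SAEs and AEs are summarised as event totals, with percentages that are shares of events: by the note for SAEs, and by cross-reference for AEs. No planned summary gives participants with at least one AE per arm. For non-serious AEs, neither the people affected nor the type can be recovered from any planned output. A stated secondary objective is therefore only partly answered. The change should be made, but efficacy conclusions do not depend on it.

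The sizes are illustrations. The range of 0.50 to 1.50 rests on assumed repeat patterns that differ by arm, and the dilution from 3.0 to 1.5 on assumed rates by type. A reader might infer that the plan would conceal a known HCQ excess, or that a participant table is sure to be precise because at least 620 per arm will be enrolled. The documents support neither. They give no AE rates for this regimen, and early stopping could leave about 280 baseline-negative participants per arm, with a half-width of 2.3 to 2.8 points for 1% v 3%.

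**What to change.** In SAP 9 and the Mock Table 1 note:

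- Report the number and percent of ITT participants in each arm with at least one SAE and with at least one AE, by worst grade. The denominator is the ITT participants in that arm. Keep event totals as a separate count.
- Add one descriptive table of participants with at least one recorded AE by type and arm: gastrointestinal, rash/skin, visual disturbance, headache, allergic reaction, hypoglycaemia, other. Keep visual disturbance and headache apart, since headache is also a COVID-19 symptom in SAP 7.1.2 and pooling would dilute a visual signal. Give arm differences with household-clustered 95% confidence intervals where counts allow.
- List non-serious AEs by arm.
- Label the table as AEs recorded under Protocol 10.2: SAEs plus AEs judged associated with study medication.

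The cost is SAP wording, one more table and a longer listing, all from AEs already on the eCRF. The downsides are some grouping of AE terms, since the documents name no coding dictionary, and several descriptive comparisons that should not be read as tests.

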10. CHANGE HISTORY

This section will Identify major changes, if any after version 1.0 approval.

Version	Activity Description
---------	----------------------

Number	Effective Date	Affected Section(s)	

Mock Table 1. Total Number of Serious Adverse Events, by Severity Grade and Arm

Severity Grade	Randomized Arm					
	HCQ		Control		Total	
	n	%	n	%	n	%
Grade 1 / mild						
Grade 2 / moderate						
Grade 3 / severe						
Grade 4 / potentially life-threatening						
Grade 5 / death						

NOTE: The denominator for calculation of percentages is the number of SAEs at a given severity level with the exception of the 'Total' column, for which the denominator is the total number of SAEs.

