11.3.2. Safety Analyses

All safety analyses will be performed on the Intention-to-Treat population. AEs and social harms will be compared by study group.

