8.1. EFFICACY AND FUTILITY MONITORING

Interim monitoring will be performed on the primary outcome after approximately 20%, 40%, 60% and 80% of expected events. Monitoring will be performed using asymmetric O'Brien-Fleming bounds for early stopping for efficacy (lower) and futility (upper). The Wald test statistic from the robust Cox model without adjustment for covariates will be using for monitoring the trial with fraction of planned households as the information fraction[1].

Table 1 Monitoring bounds with 4 interim analyses. Expected events may vary and actual stopping bound will be based on number of events observed at the time of monitoring.

Analysis	Expected number of events	Efficacy bound	Futility bound (binding)
1	19	-4.50	2.7
2	37	-3.18	0.64
3	56	-2.60	-0.52

4	74	-2.25	-1.35
5	93	-2.01	-2.01

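### The arm percentages in SAP Mock Table 1 are shares of SAE events, not risks, and no per-participant incidence of SAEs or recorded AEs over the ITT arms is specified

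*SAP*

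**What the plan says.** SAP Section 9 places all safety analyses on the ITT Cohort, which SAP 3.1 defines as every enrolled contact. It says that total numbers of SAEs and AEs "will be summarized for each randomization arm by severity grade as shown in Mock Table 1". That shell, printed after SAP Section 10, is headed "Mock Table 1. Total Number of Serious Adverse Events, by Severity Grade and Arm". It has n and % columns for HCQ, control and total, with one row per grade.

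The note sets two bases. For the arm columns, "The denominator for calculation of percentages is the number of SAEs at a given severity level"; this applies "with the exception of the 'Total' column, for which the denominator is the total number of SAEs".

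The other relevant outputs are:

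- SAP Section 9: "A line listing of SAEs will be presented by randomization arm". It also plans attribution of SAEs and AEs to study medication, and a summary of social harms by arm.
- SAP 5.1, for the CONSORT diagram: "The numbers of participants screened, screened out (with reasons for exclusion), enrolled, randomized, allocated to each study arm". The diagram also gives reasons for leaving follow-up, with adverse event as one example.
- Protocol 11.3.2: "AEs and social harms will be compared by study group". No unit, measure or test is given.

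Safety and tolerability is a secondary objective in both documents (Protocol Section 4, SAP 2.2).

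**The concern.** A percentage under an arm heading in a safety table is normally read as the proportion of that arm who had the event. Here it is not. Its denominator contains no participants, and the ITT arm size does not appear in the shell. A reader who takes 60% against 40% at face value learns nothing about how common the events were or how many people had them.

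For a prophylactic given to people who are well at entry, the absolute proportion affected in each arm is the figure that the safety objective needs. The plan does not specify it, and the percentage it does specify cannot stand in for it. The gap is wider for non-serious AEs, because the line listing covers SAEs only.

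**Working it through.** **1. Reading the note.** If the denominator were the SAEs of one grade within one arm, every filled arm cell would read 100%. The only workable reading is SAEs of that grade in both arms. With a HCQ events and b control events in a row, the cells are a/(a+b) and b/(a+b), which sum to 1 whenever a+b > 0. With T SAEs in all, the total column is (a+b)/T.

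**2. The quantity needed.** The risk in an arm is x/N, where x is the number of ITT participants with at least one event and N is the ITT arm size.

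**3. Inputs.** The documents give no safety rate, so there is no planned safety figure to reproduce and all event counts below are assumed. The arm sizes are illustrative:

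- 1000 per arm is half the ceiling of 2000 (SAP 2.1).
- 620 per arm is half of 1240 (SAP 2.4). That total reproduces as 93 / ((0.10 + 0.05)/2) = 93/0.075 = 1240. It counts baseline-negative contacts only, so the ITT arms at that enrolment would be larger and the ITT risks lower than shown.
- Early stopping could make the arms smaller: "Interim monitoring will be performed on the primary outcome after approximately 20%, 40%, 60% and 80% of expected events".

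**4. Absolute scale is lost.** With one event per person:

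| Events, HCQ v control | Printed % | Risk at 1000 per arm | Risk at 620 per arm |
|---|---|---|---|
| 6 v 4 | 60.0 v 40.0 | 0.6% v 0.4% | 0.97% v 0.65% |
| 12 v 8 | 60.0 v 40.0 | 1.2% v 0.8% | 1.94% v 1.29% |
| 120 v 80 | 60.0 v 40.0 | 12.0% v 8.0% | 19.35% v 12.90% |

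**5. Arm size enters the percentage.** Households are allocated 1:1, so participant numbers can differ between arms. Take a 2% risk in both arms, with assumed arms of 1050 and 950. The events are 0.02 × 1050 = 21 and 0.02 × 950 = 19. The row prints 21/40 = 52.5% and 19/40 = 47.5%, although the risks are equal.

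**6. Repeat events.** Let 12 HCQ events fall in 4 people and 8 control events in 8 people. The row still prints 60.0% v 40.0%. At 1000 per arm the risks are 4/1000 = 0.40% and 8/1000 = 0.80%, a ratio of 0.5 where the shares suggest 12/8 = 1.5. This is a constructed case and shows only that the table cannot reveal it.

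**7. What can be recovered.**

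- *SAEs:* if the listing identifies the participant, affected people can be counted by hand and divided by the CONSORT arm total.
- *Non-serious AEs:* the planned outputs give event totals, hence events per participant. An assumed 40 events in an arm of 1000 could lie in anywhere from 1 to 40 people, a risk between 0.1% and 4.0%. Gastrointestinal symptoms are expected (Protocol 7.2.1) and surveys are daily. Neither document says whether a recurring symptom is one event or several.

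**The case against.** The best defence is that the table is not empty of information. The n columns are printed, allocation is 1:1, and with near-equal arms 60% v 40% does indicate an event-rate ratio of about 1.5. Dividing n by the CONSORT arm total gives events per participant. This stands, so a reader who infers that the percentages say nothing about relative frequency goes too far. What they lack is absolute risk and the number of people affected.

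Four other stronger readings are tempting but not supported:

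- *That no participant-level safety figure is planned at all.* CONSORT counts people who leave follow-up because of an adverse event, and a Grade 5 count is already a count of people. Protocol 11.3.2 leaves the unit of comparison open and does not exclude participants. But a disposition count is not AE incidence: Protocol 7.4 and 8.1 keep people who stop study drug in follow-up, so most intolerance would not appear there.
- *That the AE denominator is wholly undefined.* Section 9 sends AEs to the same shell, so by analogy it is the AEs of that grade. The title and note naming only SAEs is an editorial gap; the analogy carries the same limitation over to AEs.
- *That two bases in one row is an error.* The note discloses it. It is a layout choice, though the three percentages are not comparable with one another.
- *That the trial's conclusions are at risk.* The primary analysis, sample size and monitoring bounds do not use this table.

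It may also be said that this is only a mock shell. Section 9 makes the shell the specification, and nothing else in the plan defines the summary.

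**Conclusion.** The point holds as a reporting gap in a secondary objective, worth correcting before database lock. By the stated rule, the arm percentages are shares of SAE events. They fix the ratio of event counts but not the risk: the same 60% v 40% fits HCQ risks from 0.6% to 12.0% at 1000 per arm under the assumed counts. They also depend on arm sizes and on repeat events. Neither document specifies the proportion of ITT participants with at least one SAE or recorded AE. For SAEs this is an inconvenience, because a partial reconstruction is possible. For non-serious AEs the number of people affected is missing from the planned outputs, although the underlying records exist.

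The reading of the note and the 100% row sum need no assumption. The numerical sizes rest on invented counts and illustrative arm sizes; they are examples, not bounds or forecasts.

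**What to change.** Change the Mock Table 1 note and SAP Section 9 as follows.

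- For each arm, report the number and percentage of ITT participants with at least one SAE, classified by highest grade. Use the ITT arm N, printed in the column header, as the denominator.
- Add a second table with its own title and note that does the same for recorded AEs. Label it that way because Protocol 10.2 requires eCRF entry only of SAEs and of AEs judged by participant or clinician to be linked to study medication.
- Keep event counts alongside, without percentages.
- A between-arm risk difference is optional. If one is given, its interval should allow for household clustering, because allocation is by household (Protocol 7.5).

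The cost is one revised shell and note, one added shell, and a sentence in Section 9. No new data are needed.
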